8. SAFETY REPORTING

Adverse events will be recorded and reported in accordance with University Hospitals Bristol's Research Safety Reporting SOP. The trial steering committee will periodically review all serious adverse events. Serious adverse events will be collected until the infant is discharged home. As parental participation is limited to filling in Edinburgh postnatal depression scale, mother-to-infant

bonding scale and paternal postnatal attachment scale, no adverse event or serious adverse event recording or reporting will be conducted for this group.

8.1 Adverse event (AE)

An adverse event (AE) is any undesirable event in a subject receiving treatment according to the protocol, including occurrences which are not necessarily caused by or related to administration of the research procedures.

8.2 Serious Adverse Events (SAE)

An SAE is any untoward medical occurrence that:

- results in death
- is life-threatening
- requires inpatient hospitalisation or prolongation of existing hospitalisation
- results in persistent or significant disability/incapacity
- consists of a congenital anomaly or birth defect

*Life threatening in the definition of an SAE refers to an event in which the subject was at risk of death at the time of the event; it does not refer to an event that hypothetically might have caused death if it were more severe. Medical judgement should be exercised in deciding whether an AE is serious. SAE that are not immediately life-threatening or do not result in death or hospitalisation but may jeopardise the subject or may require intervention to prevent one or the other outcomes listed in the definition above, should also be considered serious.

8.3 Suspected unexpected serious adverse reaction (SUSAR)

An SAE that occurs and is

- "Related" that is, possibly, probably or definitely resulted from administration of any of the research procedures, and
- "Unexpected" that is, the type of event is not listed in the protocol as an expected occurrence.

8.4 Assessment of Adverse events

All adverse events will be assessed as follows:

8.4.1 Intensity assessment

- The assessment of intensity will be based on the investigator's clinical judgement using the following definitions:
- Mild: An event that is easily tolerated by the patient, causing minimal discomfort and not interfering with everyday activities.
- Moderate: An event that is sufficiently discomforting to interfere with normal everyday activities.
- Severe: An event that prevents normal everyday activities.

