7.1.1 Inclusion criteria

- Newborn infants born at gestation ≥ 36+0 weeks
- undergoing whole-body cooling for hypoxic-ischemic encephalopathy as per the national and south west neonatal network cooling therapy pathway and their parents who consent to participate in the study.
- cooling provided by a cooling device offering servo-controlled cooling using a wrap or blanket covering the whole body.
- receiving intensive care and will have probes monitoring core temperature and scalp EEG electrodes, may have central or peripheral arterial or venous catheter and may have a urinary catheter.

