9.2 Assessment and management of risk

Potential risks to the participants include the adverse effects identified in the protocol for the babies. These include dislodgement of endotracheal tube and arterial or venous catheters. Appropriate techniques that will prevent these happening will be developed in stage 1. In our current family centred cuddling practice these adverse incidents are extremely rare. If an adverse incident occurs, babies

can be quickly transferred in to the incubator and airway or the site of arterial access can be secured preventing any potential harm to the babies. The research nurse running the study is an experienced senior advanced neonatal nurse practitioner who is competent in anticipating any of these potential risks and managing them.

Some parents may feel uncomfortable to hold their sick baby being connected to several intensive care monitors. Their baby's skin will feel cold and they will be sedated to counteract the distress induced by cooling. Holding their cold baby may be emotionally challenging to some parents. In our current standard practice, parents are familiarised with all the intensive care monitoring that their babies receive, and parents touch their baby including the cooling wrap covering their body. This will familiarise the parents with their baby before they cuddle their baby.

Mothers will be completing the Edinburgh postnatal depression scale. If the questionnaire identifies that the scores reach the threshold for further evaluation, we will discuss the result with the woman and ask if she is ok to be referred to the perinatal mental health team for support. In both recruiting sites, parents of babies receiving intensive care needing psychology or mental health support are identified during the weekly social care rounds. A referral will be made to the perinatal psychologist/mental health team, who then offers the parents a convenient appointment. Furthermore, a family support worker supports all families who have their babies admitted in the neonatal intensive care unit.

In the standard practice of cuddling, we have not identified any potential risks to the nursing team. However, if any potential adverse event occurs during the cuddling process, appropriate debrief sessions will be used to mitigate any potential emotional distress to the staff involved.

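### The adverse-event intensity scale in section 8.4.1 is poorly anchored for newborns in intensive care, so moderate and severe cannot be reliably told apart for events during cooling

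*Protocol*

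**What the plan says.** Section 8.4 applies its assessment to every event: "All adverse events will be assessed as follows". Section 8.4.1 then fixes how intensity is judged: "The assessment of intensity will be based on the investigator's clinical judgement using the following definitions".

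Three grades follow. The lowest joins tolerance, discomfort and activities: "Mild: An event that is easily tolerated by the patient, causing minimal discomfort and not interfering with everyday activities". The middle grade leaves tolerance out and ties discomfort to its effect on activities: "Moderate: An event that is sufficiently discomforting to interfere with normal everyday activities". The highest grade leaves out discomfort as well, so that one criterion remains: "Severe: An event that prevents normal everyday activities".

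On who is graded, section 8 says of parents that "no adverse event or serious adverse event recording or reporting will be conducted for this group". On the state of the infants, the inclusion criteria (7.1.1) require that they are "receiving intensive care and will have probes monitoring core temperature and scalp EEG electrodes", and section 9.2 says that "they will be sedated to counteract the distress induced by cooling".

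The protocol gives no neonatal version of the scale and no physiological or treatment-based anchor for the three grades.

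**The concern.** The scale presumes a patient with a normal daily routine that an event can disturb or stop. A sedated infant in intensive care has no obvious counterpart to that routine. The events this study most needs to describe are of a different kind: a tube or line coming out during the move, or a fall in blood pressure.

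Safety is part of the second objective (4.1). The Study Summary promises a detailed description of adverse events, and the steering group reviews those events when it advises on continuation. If the intensity grade attached to an event depends mainly on how an assessor chooses to interpret the scale, that part of the description carries little information.

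**Working it through.** No arithmetic applies, because section 8.4.1 contains no figure. The check sets the definitions against the population and then against each use of adverse-event data.

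**1. Who is graded.** All adverse events are graded (8.4). Parents are excluded from recording (8). The graded subject is therefore the infant.

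**2. What each grade requires.**

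| Grade | Tolerance | Discomfort | Everyday activities |
|---|---|---|---|
| Mild | easily tolerated | minimal | no interference |
| Moderate | not mentioned | enough to interfere | interfered with |
| Severe | not mentioned | not mentioned | prevented |

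Mild has three joint conditions, and the first two can be judged by an observer. The step from moderate to severe is a step from interference with everyday activities to their prevention. It has no other criterion apart from the discomfort element in moderate.

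**3. Apply this to events during cooling.** Take three events that the protocol itself lists: accidental extubation and vascular catheter dislodgement (8.6), and hypotension (8.5). An assessor can say whether the infant tolerated the event easily, so mild can often be ruled in or out. If it is ruled out, the assessor must decide whether the event interfered with everyday activities or prevented them. For an infant who is sedated, cooled and in intensive care, the text gives no basis for that decision.

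**4. Apply this to events after cooling.** Serious adverse events are collected until discharge home (8), and difficulty establishing feeding is on the expected list (8.5). Feeding is a normal infant activity, so interference with it has an ordinary meaning. The problem is concentrated in the cooling period, which is when most of the intervention takes place.

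**5. Trace where the grade is used.**

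| Use of adverse-event data | What it depends on | Uses the intensity grade? |
|---|---|---|
| Seriousness (8.2) | death, threat to life, hospitalisation, disability, need for intervention | No |
| Cuddle stop rules (5.1.1.5) | physiological thresholds and durations, or staff concern | No |
| Reporting to sponsor (8.5, 8.7) | seriousness, relatedness, expectedness; all deaths | No |
| Green, Orange and Red zones (section 3) | presence and modifiability of adverse effects | No |
| Outcomes (Study Summary, flow chart, 4.2) | incidence, rate, type, description | Not named |
| Events of interest (8.6) | frequency | No |

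The grade therefore feeds only the descriptive account of events: the summary under Stage 2 Data Analysis and any steering-group report that carries it.

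**6. Is the wording deliberate?** Section 8.4.2 refers to a product and to rechallenge, although the intervention is a cuddle. This suggests that section 8.4 is generic wording not adapted to this study. It is an inference and not needed for the conclusion.

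**The case against.** The best defence is that intensity is left to clinical judgement, not to self-report, so an infant's inability to describe discomfort does not matter. The protocol also records an observer-rated neonatal pain, agitation and sedation score (5.1.1.1). With 20-24 infants in Stage 2, each event can be described individually, and a reader need not rely on the grade.

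Much of this stands, and it limits the consequence. It does not remove the defect. The judgement has to be exercised through the stated definitions. The neonatal score is listed with the baseline data, is not linked to event grading, and could inform only the discomfort element.

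Several stronger conclusions are tempting, but the protocol does not support them:

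- A reader might infer that an extubation could be graded anywhere from mild to severe. Mild also requires that the event be easily tolerated, so an extubation that destabilises a ventilated infant does not qualify. Severe requires that the event itself do the preventing, so pre-existing sedation does not push every event to the top grade.
- A reader might infer that the Orange and Red zones turn on the grade. They turn on whether adverse effects can be modified.
- A reader might infer that an event needing resuscitation could be lost among trivial ones. Section 8.2 captures it as serious whatever its intensity grade.
- A reader might call the grades arbitrary. Judgement can still separate mild from the rest, and later events can be graded more naturally. The supportable statement is that the scale is poorly anchored and unlikely to be reproducible between assessors.
- A reader might assume a severity table or a comparison of grades between the two sites. The protocol promises neither.

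**Conclusion.** The point holds in a limited form. The scale in 8.4.1 does not fit the infants to whom it is applied. Its moderate and severe grades cannot be reliably distinguished for events during cooling, and grades are unlikely to agree between assessors. Every graded event passes through this scale, across 4-6 infants in Stage 1 and 20-24 in Stage 2 (24 to 30 in all, from 4 + 20 and 6 + 24), but the difficulty is greatest for events during cooling.

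The consequence is confined to one descriptor in the adverse-event account. No outcome, stop rule, reporting duty or progression decision changes. The correction is still worth making: it is cheap, and a small descriptive safety study depends on describing its events well.

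This rests on two assumptions: that no adverse-event form or sponsor procedure outside the protocol redefines the grades for neonates, and that assessors follow the definitions as written. The size of the disagreement between assessors cannot be estimated from the protocol.

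**What to change.** Replace the three definitions in 8.4.1 with criteria that can be observed in a neonate, for example:

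- **Mild:** no change in care beyond monitoring.
- **Moderate:** a minor or temporary change in care.
- **Severe:** a major change in care or escalation of intensive care.

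Add a brief graded example for each listed device event, so that assessors at both sites start from the same reference. Leave the seriousness criteria in 8.2 unchanged. This changes only how an event is described, not how any infant is managed.

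The information needed is already planned. The flow chart lists escalation of intensive care among the adverse events, and the data collection section covers ventilation and cardiovascular measurements, drug doses and infusions.

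The cost is new wording in 8.4.1 and on the adverse-event form, a short re-briefing of assessors, and regrading of any events already graded. Some judgement between minor and major changes will remain; the examples reduce it but do not remove it.

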8.4.2 Causality

- Not related: Temporal relationship of the onset of the event, relative to administration of the intervention, is not reasonable or another cause can by itself explain the occurrence of the event.
- Unlikely: Temporal relationship of the onset of the event, relative to administration of the intervention, is likely to have another cause which can by itself explain the occurrence of the event.
- *Possibly related: Temporal relationship of the onset of the event, relative to administration of the intervention, is reasonable but the event could have been due to another, equally likely cause.
- *Probably related: Temporal relationship of the onset of the event, relative to administration of the intervention, is reasonable and the event is more likely explained by the product than any other cause.
- *Definitely related: Temporal relationship of the onset of the event, relative to administration of the intervention, is reasonable and there is no other cause to explain the event, or a rechallenge (if feasible) is positive.

*Where an event is assessed as possibly related, probably related, or definitely related the event is an adverse reaction"

8.5 Expected Adverse Events

In neonates with HIE, adverse events are not unexpected and are not infrequent. The following list of events are 'anticipated' as part of the signs and symptoms of HIE and will not be reported to the Sponsor if the event is classified as serious, unless deemed related to intervention. All other SAEs will be reported to Sponsor within 24 hours of the team becoming aware of the event. :

Seizures

Hypotension

Coagulopathy

Renal impairment with decreased urine output Liver impairment Difficulty establishing feeding Abnormalities in neuroimaging Sepsis / infection Thrombocytopenia Hyponatraemia Hypoglycaemia Pneumothorax Necrotizing enterocolitis

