5.1.1.5 Stop rules for the cuddle

Cuddle will be stopped, and the baby transferred back to the cot, if any of the following occurs continuously for 5 to10 minutes during cooling without responding to any potential resolvable causes:

- 1. Rectal temperature < 30.0°C or >35.0°C
- 2. Mean blood pressure < 30mmHg or > 75 mmHg
- 3. Heart rate < 50 beats per minute
- 4. Heart rate >180 beats per minute
- 5. Oxygen saturation < 80%
- 6. Fraction of inspired oxygen >70%
- 7. Electroclinical or electrical status epilepticus

If any of the following occurs for greater than 20 minutes after any remediable causes are attended to:

- Rectal temperature between 30.0 and 32.9°C or between 34.1 and 34.9°C
- Mean blood pressure 10 mmHg below or above the pre-cuddle period
- Heart rate <20 beats per minute from the pre-Cuddle period or >20 beats per minute from the pre-Cuddle period
- Oxygen Saturation 80-88%
- Increase in Fraction of inspired oxygen by 20% above the pre-CoolCuddle period

or

• Medical or nursing concern that the infant is not adequately supported

If cuddle is undertaken during the rewarming period, the following stop rules will apply if they occur continuously for 5 to 10 mins despite attending to the potentially remediable actions:

- 1. Mean blood pressure < 30 mmHg or > 75 mmHg
- 2. Heart rate < 50 beats per minute
- 3. Heart rate > 180 beats per minute
- 4. Oxygen saturation < 80%
- 5. Fraction of inspired oxygen >70%
- 6. Electroclinical or electrical status epilepticus

The following stop rules will apply during the rewarming period, if they persist for greater than 20 minutes after any remediable causes are attended to:

- Rectal temperature greater than 4.0°C or less than 4.0°C from the pre-CoolCuddle period
- Heart rate 30 beats per min above or below the pre-CoolCuddle period
- Mean Blood pressure 20mmHg above or below the pre-CoolCuddle period
- Oxygen saturation 80-88% below the pre-CoolCuddle period
- Increase in Fraction of inspired oxygen by 20% above the pre-CoolCuddle period

Or

Medical or nursing concern that the infant is not adequately supported

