8.7 Reporting procedures for serious adverse events

Unexpected SAEs and SAEs assessed as causally related to the cuddling intervention must be reported to the sponsor within 24 hours of a member of the research team becoming aware of it in accordance with University Hospitals Bristol's Research Safety Reporting SOP.

All deaths regardless of causality must be reported to Sponsor.

All Serious Adverse Events will be reported to the study steering group in the form of a periodic report and discussed at each study steering group meeting.

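### A serious listed event that begins during a cuddle can be graded either *Not related* (no sponsor report) or *Possibly related* (24-hour report), because the causality categories overlap and the exemption ignores onset time

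*Protocol*

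**What the plan says.** Section 8.5 introduces its list with the words "The following list of events are 'anticipated' as part of the signs and symptoms of HIE". Events on it "will not be reported to the Sponsor if the event is classified as serious, unless deemed related to intervention"; every other serious adverse event goes to the sponsor within 24 hours. The list has 13 entries. It opens with seizures and hypotension and closes with "Hyponatraemia Hypoglycaemia Pneumothorax Necrotizing enterocolitis". Nothing in the section refers to when the event began.

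Section 8.7 agrees with 8.5: "Unexpected SAEs and SAEs assessed as causally related to the cuddling intervention must be reported to the sponsor within 24 hours". It adds that all deaths go to the sponsor and that all serious adverse events go to the steering group in periodic reports.

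Section 8.4.2 grades an event *Not related* when the timing "is not reasonable or another cause can by itself explain the occurrence of the event". *Unlikely* also rests on another cause that suffices by itself. *Possibly related* applies when the timing is reasonable and another cause is equally likely. That grade and the two above it count as adverse reactions.

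**The concern.** The study asks whether cuddling destabilises cooled infants, and it has no concurrent control group. A serious acute event that begins while the infant is being held, or shortly afterwards, is among the most informative safety signals it can produce.

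Several such events are on the exempt list. Hypotension and seizures overlap with the stop rules in 5.1.1.5, which include a lower limit for mean blood pressure and "Electroclinical or electrical status epilepticus". Hypoglycaemia overlaps with the blood gas, including glucose, taken before and after the cuddle. For these events the causality grade alone decides whether a 24-hour report is made, and the grading text does not settle the grade.

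The grade may also matter later. The green zone in Section 3 turns on there being no adverse effects with the cuddle protocol, and ambiguous attribution can feed into that judgement.

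**Working it through.** There is no figure in the plan to reproduce. The check sets the sections side by side and follows one event through them.

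**1. Which listed events overlap with what the cuddle is monitored for?**

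| Event listed in 8.5 | Stop rule (5.1.1.5) | Pre/post cuddle measure |
|---|---|---|
| Hypotension | Yes, low blood pressure side | Blood pressure every 5 minutes |
| Seizures | In part, status epilepticus only | aEEG analysed offline for seizures |
| Hypoglycaemia | No | Glucose in the pre and post blood gas |
| Pneumothorax | No | None named |

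Of the seven stop rules that apply over 5 to 10 minutes during cooling, two touch a listed event. The other five (rectal temperature, low heart rate, high heart rate, saturation, inspired oxygen) match no listed event by name. Serious events of those kinds fall under the 24-hour rule.

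**2. Grade one event.** Take serious hypotension that starts during a cuddle in an infant with HIE.

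- *Not related*: the definition has two limbs joined by 'or'. The timing limb fails, because onset during the cuddle is reasonable timing. The second limb can be met because HIE can explain hypotension, which is why it is listed. Result: no sponsor report.
- *Unlikely*: met if HIE is judged the likely and sufficient cause. This is not an adverse reaction. Result: no sponsor report.
- *Possibly related*: met if HIE and the cuddle are judged equally likely. This is an adverse reaction. Result: report within 24 hours.

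The overlap is structural. An event that could have been due to an equally likely other cause is, on a plain reading, one that the other cause can explain by itself. The second limb of *Not related* has no likelihood threshold to separate the two grades.

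**3. What other routes exist?**

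- Steering group: periodic reports of all adverse events and all serious adverse events, with no causality filter, and four meetings. The planned period, 1 September 2019 to 1 April 2021, is 19 months. The spacing of meetings is not stated. If even, the gap is about 19 / 4 = 4.75 months; if one meeting falls at the start and one at the end, 19 / 3 = 6.3 months. How often written reports go out between meetings is not stated either.
- Stopped cuddles: Section 5 (Stage 2, Data Analysis) treats each as an adverse event to be fully investigated. The numeric rules need persistence for 5 to 10 or more than 20 minutes. Hypoglycaemia and brief seizures are not named criteria, and an event that starts in the post-cuddle epoch stops no cuddle. The rule on medical or nursing concern may catch some of these.
- Sponsor: deaths always; listed non-fatal serious events only if deemed related.

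**4. How large would a reporting window be?** A full cuddle of 2 hours plus a post-cuddle epoch of 30 to 60 minutes is 2.5 to 3 hours, plus the move itself. Cooling for 72 hours plus rewarming for 6 to 8 hours is 78 to 80 hours. One full-length cuddle therefore covers between 2.5 / 80 = 3.1% and 3 / 78 = 3.8% of that period. More cuddles raise the share in proportion.

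**The case against.** The strongest reply is that the design is coherent. A disease-based list with an exception for related events is a recognisable approach, and 8.5 and 8.7 agree with each other. The exemption is conditional, since *Possibly related* is enough to restore the 24-hour report. The *Not related* wording can be read as a judgement on the particular event, not on whether HIE could cause such events in general. The sponsor's Research Safety Reporting SOP, which is not at hand, may guide grading.

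The data are also well protected. The independent steering group sees everything, stopped cuddles are investigated, the frequency of stop-rule use is an outcome in 4.2, and blood pressure and aEEG are recorded across the epochs.

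Most of this stands, and it rules out several stronger readings:

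- A reader might infer that the wording forces *Not related* for every listed event. It does not. It permits that grade, and it equally permits *Possibly related*.
- A reader might infer that these harms disappear from the study. They do not. Only expedited sponsor review is at risk.
- A reader might infer that the list covers whatever the stop rules watch for. Only hypotension and status epilepticus do so. Pneumothorax is neither a stop rule nor a named pre/post measure.
- A reader might infer harm from 8.3, where an event is unexpected only if "the type of event is not listed in the protocol as an expected occurrence", so that a related serious seizure cannot be a SUSAR. That is so, but it alters no report, because 8.7 already sends related serious events to the sponsor whether or not they are expected.

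The reply does not resolve the overlap in 8.4.2 or the absence of any onset-time condition in 8.5.

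**Conclusion.** The point holds in this form: for a serious, non-fatal, listed event with onset during or just after a cuddle, the protocol's text supports both a 24-hour sponsor report and no sponsor report. The events most affected are hypotension and seizures, then hypoglycaemia.

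The consequence is possible loss of expedited sponsor review. The remaining steering group route is periodic, with meetings roughly 5 to 6 months apart if evenly spaced. That spacing is an assumption. The early-termination provision needs the sponsor's agreement as well as the steering group's instruction, so the sponsor's timely knowledge matters.

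How often grading would go one way or the other cannot be estimated from the protocol, and the SOP might narrow the ambiguity. The point should be corrected, but it does not undermine the study's data.

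**What to change.** 1. **Section 8.4.2.** Make the categories mutually exclusive. Where the timing is reasonable, a possible alternative cause such as HIE should not be sufficient for *Not related*. Correct *Unlikely* in the same way, since it rests on the same sufficient-cause phrase and its stated temporal criterion is incomplete. One workable order is to judge timing first and then, if it is reasonable, grade by the relative likelihood of the causes.
2. **Section 8.5.** Limit the exemption to listed events with onset outside the window that runs from the start of the move to the parent to the end of the post-cuddle epoch. Listed serious events that begin or worsen inside it go to the sponsor within 24 hours, whatever the causality grade. Change 1 alone is not enough, because an *Unlikely* grade would still remove the report.
3. **SAE form.** Add one field for onset time relative to the cuddle.

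Section 8.6 already ties its events of interest to the cuddling process, so a window follows the protocol's own approach. Section 8.3 needs no change for this purpose.

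The cost is wording in two sections, one form field and a few extra expedited reports. With 20 to 24 infants in Stage 2 and a window of about 3 to 4% of the cooling and rewarming period per full-length cuddle, the added load should be small. Clinical care is unchanged.
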